4.8.1.2 Key Secondary Analyses

The three key secondary endpoints are: 1) EULAR response (good) rate at Day 8, 2) EULAR response (good and moderate combined) rate at Day 15, and 3) EULAR response (good) rate at Day 15. Both comparisons (Nanocort 150 mg vs. Depo-Medrol[®], and Nanocort 75 mg vs. Depo-Medrol[®]) will be completed for each of the three key secondary endpoints (i.e., up to 6 key secondary analyses).

The key secondary hypotheses will only be tested if at least one primary analysis is significant. If for one of the dosages the primary analyses is not significant, then the corresponding key secondary hypotheses will not be tested. The key secondary hypotheses will be tested with a two-sided confidence level, α_s . The calculation of α_s depends on the maximum p-value from the primary hypotheses, the significance of the primary hypotheses and α_p .

Step 1: The primary hypotheses are tested using Hochberg procedure at $\alpha_p = 0.045 < \alpha$ (0.05). If at least one of the primary null hypotheses is rejected then go to Step 2. The significance value for Step 2 (α_s) is a function of largest primary p-value.

Step 2: Test the secondary null hypotheses using Hochberg procedure at α_s .

$$\begin{aligned}\alpha_s &= \min(\lambda \alpha^*/(p^*)^2, \alpha_p) && \text{if } p^* > \alpha_p \text{ and} \\ \alpha_s &= \alpha && \text{if } p^* \leq \alpha_p\end{aligned}$$

[figure not shown]
Where p^* is the largest primary p-value, λ is chosen to control the global FWER at the alpha level.

$$\begin{aligned}\alpha^* &= \alpha_p(1 - \sqrt{2 - \alpha_p/(k_1 - 1)} - \alpha / \alpha_p)^2 && \text{if } \alpha' \leq \alpha \\ &= \alpha_p(\alpha - \alpha_p) / (k_1 - 1 - \alpha_p) && \text{if } \alpha' > \alpha\end{aligned}$$

Where $\alpha' = \alpha_p + \alpha_p^2 / (k_1 - 1) - \alpha_p^3 / (k_1 - 1)^2$

K_1 = Number of primary endpoints (in this case $k_1 = 2$)

The significance level carried over to α_s depends on the magnitude of the primary p-values rather than the number of significant primary p-values. This method assumes a full parametric model. The joint distribution of the hypotheses in primary and secondary endpoints is considered to calculate λ . If the joint distribution of the test statistic is not specified, the λ parameter is chosen under the worst-case scenario.

The key secondary analyses will be completed for the ITT and PP populations.

4.8.2 Simplified Analyses

The primary and key secondary analyses will be completed using the Hochberg and gatekeeping methodology described above but will also be analyzed using simple chi-square tests.

The simplified analyses will be completed for the ITT and PP populations.

4.8.3 Other Secondary Analyses

All other secondary analyses will be completed for both the ITT and PP populations. EULAR response (good, moderate, no response) at Week 1, 2, 3, 4, 6, 8 and 12 will be summarized by treatment group and the treatment groups will be compared by using the non-parametric Wilcoxon-Mann-Whitney test.

DAS28 will be summarized and analyzed at Week 1, 2, 3, 4, 6, 8 and 12. The DAS28 score is calculated as follows:

$$DAS28 = (0.555 \times \sqrt{TJC}) + (0.284 \times \sqrt{SJC}) + (0.7 \times \log_e ESR) + (0.0142 \times GH)$$

where TJC = tender joint counts on 28 joints, SJC = swollen joint counts on 28 joints, GH = general health, i.e. patient's global assessment of disease activity (100 mm VAS) and ESR = erythrocyte sedimentation rate (mm/hr). If ESR was not available, then CRP may be used instead. See Appendix C for details on scoring and coding. At a particular timepoint, if one or more of the four components used in calculating DAS28 are missing, then the DAS28 will be considered missing at that timepoint.

If DAS28 scores are approximately normally distributed via visual inspection, then DAS28 scores at 1, 2, 3, 4, 6, 8 and 12 weeks will be analyzed using analysis of covariance (ANCOVA), including baseline scores and study site as covariates. If DAS28 scores are markedly non-normally distributed via visual inspection, then the Kruskal-Wallis test will be used to compare the groups at each time point. In addition to the group comparison, the time course of DAS28 scores will be submitted to a repeated measures analysis of variance, with treatment group, time and the interaction of treatment group and time in the model.

If the percentage change in DAS28 scores is approximately normally distributed via visual inspection, then % change at 1, 2, 3, 4, 6, 8 and 12 weeks will be analyzed using ANCOVA, including baseline scores and study site as covariates. If % change is markedly non-normally distributed via visual inspection, then the Kruskal-Wallis test will be used to compare the groups at each time point. In addition to the group comparison, the time course of % change will be submitted to a repeated measures analysis of variance, with treatment group, time and the interaction of treatment group and time in the model.

Time to first EULAR response (moderate or good) will be analyzed using the Kaplan-Meier method; comparison between the treatment groups will be performed using the log-rank test.

American College of Rheumatology (ACR) 20/50/70 response at week 1, 2, 3, 4, 6, 8 and 12 will be summarized and analyzed. See Appendix D for details on scoring and coding. ACR score is a scale to measure change in rheumatoid arthritis symptoms. It is named after the American College of Rheumatology. Different degrees of improvement are referred to as ACR20, ACR50, ACR70. The following definition of improvement was selected: 20% improvement in tender and swollen joint counts and 20% improvement in 3 of the 5 remaining ACR core set measures: patient and physician global assessments, pain, disability, and an acute-phase reactant [23]. ACR 50 and ACR 70 criteria are defined in a manner similar to that for ACR 20, but with improvement of at least 50 percent and 70 percent in the individual measures, respectively. The comparison of ACR20,

ACR50 and ACR70 response rates among treatment groups will be analyzed using a stratified Cochrane-Mantel-Haenszel test.

Tender and swollen joint counts at week 1, 2, 3, 4, 6, 8 and 12 will be summarized. The DAS28 score and the EULAR Response incorporate the tender and swollen joint counts. For this reason, no formal testing will be done between the three treatment groups.

Four Visual Analog Scores (VAS) will be summarized and analyzed at week 1, 2, 3, 4, 6, 8 and 12 including: 1) patient VAS value for experience of pain, 2) patient VAS value for General Health, 3) patient VAS value for RA activity, and 4) investigator VAS value for RA activity.

If the change from baseline in VAS is approximately normally distributed via visual inspection, then the change from baseline in VAS at 1, 2, 3, 4, 6, 8 and 12 weeks will be analyzed using ANCOVA, including baseline scores and study site as covariates. If the change from baseline in VAS is markedly non-normally distributed via visual inspection, then the Kruskal-Wallis test will be used to compare the groups at each time point.

Short Form 36 (SF-36) to assess physical and mental component at baseline, week 1, 2, 4, 6, and 12 will be summarized and analyzed. See Appendix A for details on scoring and coding. If the change from baseline is approximately normally distributed via visual inspection, then the change from baseline at 1, 2, 3, 4, 6, 8 and 12 weeks will be analyzed using ANCOVA, including baseline scores, age and gender as covariates. If the change from baseline is markedly non-normally distributed via visual inspection, then the Kruskal-Wallis test will be used to compare the groups at each time point.

Health Assessment Questionnaire (HAQ) at baseline, week 1, 2, 3, 4, 6, 8 and 12 will be summarized and analyzed. See Appendix E for details on scoring and coding. If the change from baseline is approximately normally distributed via visual inspection, then the change from baseline at 1, 2, 3, 4, 6, 8 and 12 weeks will be analyzed using ANCOVA, including baseline HAQ, baseline DAS28 and study site as covariates. If the change from baseline is markedly non-normally distributed via

visual inspection, then the Kruskal-Wallis test will be used to compare the groups at each time point.

FACIT Fatigue Scale at baseline, week 4 and 6 will be summarized and analyzed. See Appendix F for details on scoring and coding. If the change from baseline is approximately normally distributed via visual inspection, then the change from baseline at 1, 2, 3, 4, 6, 8 and 12 weeks will be analyzed using ANCOVA, including baseline FACIT, baseline DAS28 and study site as covariates. If the change from baseline is markedly non-normally distributed via visual inspection, then the Kruskal-Wallis test will be used to compare the groups at each time point.

Maintenance of Improvement at 12 Weeks assessed during a blinded review by the Medical Monitor (MM) and Principal Investigator (PI) at the end of the study will be compared between treatment groups using a stratified Cochrane-Mantel-Haenszel test, stratified by study site.

The Health Economics Questionnaire (HEQ) at week 12 will be summarized in a table of the responses for each treatment group as recorded on the questionnaire.

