8.2 Randomisation, blinding and treatment allocation

Subject randomization will take place before the start of administration of the IMP.

Subjects will be randomized in a 1:1:1 ratio to the three treatment arms and stratified by site.

Randomization of the subjects will be performed by an Interactive Web-based Randomization System (IWRS) by an independent party. The randomization number will be recorded on the eCRF. Once the numbers have been assigned they cannot be reassigned.

Subjects in this trial will be randomized in a 1:1:1 ratio to receive one of three dose groups:

- **Nanocort 75 mg** IV infusion and IM saline injection on Day 1 and Day 15, or
- **Nanocort 150 mg** IV infusion and IM saline injection on Day 1 and Day 15, or
- **Depo-Medrol 120 mg** IM injection and IV saline infusion on Day 1 and Day 15

Blinding:

Prior to the start of the study, a copy of the master randomization code will be stored in confidential manner up to the unblinding after database lock. A separate unblinded Pharmacovigilance Medical Reviewer and unblinded Pharmacovigilance Associate will be available for triage, review and submission of safety events.

Any reported Suspected Unexpected Serious Adverse Reactions (SUSARs) will be triaged by the Medical Monitor in a blinded fashion and forwarded for full processing to the unblinded Medical Reviewer and unblinded Pharmacovigilance Reviewer for processing and reporting to the Competent Authority (CA) and Independent Ethics Committee (IEC) per regulations.

Unblinding to Investigator and subject will occur only after database closure at the end of the study. The study blind will only be broken after database lock except in the case of

emergency to protect subject's safety. The code may be broken in case of an emergency, preferably after discussion with the MM. Any code break will be recorded and a copy retained within the study file.

The blind will be preserved throughout the study unless, in the opinion of the Investigator, the lack of this information places the subject at undue risk. In general, this will occur only if an adverse event occurs for which the subject's physician requires knowledge of the treatment assigned. In this case, the Sponsor should be notified as soon as possible and un-blinded information for the subject's treatment group will be provided.

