4.2 Missing Data Handling

Imputation will be implemented for partial start/end dates of adverse events dates. If the start day is missing, impute the 1st of the month, unless month and year are the same as month and year of the first dose of study drug then impute the first dose date. If start day and start month are both missing, impute 1st January but if year is the same as year of the first dose date, then impute first dose date. If the end day is missing, impute the last day of the month. If end day and end month are both missing impute 31st December. No other imputation of missing data will be performed, and only available data will be presented.

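### The repeated-measures model of DAS28 score omits baseline DAS28, so its treatment main effect and visit-level contrasts lose precision and carry chance baseline imbalance

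*Combined protocol and SAP*

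**What the plan says.** SAP 4.8.3 plans two kinds of between-group analysis of DAS28 score at Weeks 1, 2, 3, 4, 6, 8 and 12.

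- **Visit by visit.** If the scores look approximately normal, they are to be "analyzed using analysis of covariance (ANCOVA), including baseline scores and study site as covariates". If they look markedly non-normal, a Kruskal-Wallis test at each visit replaces the ANCOVA.
- **Over time.** The next sentence begins "In addition to the group comparison, the time course of DAS28 scores will be submitted to a" and continues "repeated measures analysis of variance, with treatment group, time and the interaction of treatment group and time in the model". Neither baseline DAS28 nor site is named.

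The next paragraph repeats this for percentage change: "the time course of % change will be submitted to a repeated measures analysis of variance", with the same three terms.

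Protocol 10.4.2 gives baseline and site for the ANCOVA and lists no terms for the repeated-measures analysis. SAP 4.11, which lists departures from the protocol, does not mention this model. Site is the stratification factor (Protocol 8.2: "Subjects will be randomized in a 1:1:1 ratio to the three treatment arms and stratified by site"). The SAP does not say whether baseline is one of the levels of time, which fitting method is used, or what covariance structure applies.

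**The concern.** Two analyses of one endpoint, a sentence apart, treat baseline differently, and no reason is given. Baseline DAS28 is collected on every subject before dosing and can be expected to correlate with later DAS28. Leaving it out of a model for raw scores puts between-subject variation that could be explained into the error term. Any chance difference between arms at Day 1 also passes into the treatment effect.

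Both effects matter more in a small trial, and SAP 4.1 says the sample will be much less than planned because the study stopped early. If the Kruskal-Wallis fallback is triggered, neither the visit-wise comparison nor the repeated-measures model of raw DAS28 would adjust for baseline.

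**Working it through.** **Stated figures.** The documents give no power, SD or precision figure for this analysis. The only sample-size arithmetic that can be checked is 3 × 110 = 330, and 99 / 0.90 = 110 for about 10% drop-out (Protocol 4.4). Neither bears on this model.

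**Inputs.** The number of post-baseline visits is m = 7 (SAP 4.8.3). The following are assumptions, because the documents give no values: compound symmetry with one correlation ρ of 0.3, 0.5 or 0.7 between any two DAS28 measurements, including baseline; equal variance (1 SD²) at every visit; a true difference of 0.4 SD; and 33 per arm (0.30 × 110) to represent the shortened trial.

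**Variance of a subject's seven-visit mean (in SD²).**
- Without baseline: V₀ = [1 + (m − 1)ρ] / m
- With baseline as covariate: V₁ = V₀ − ρ²
- SE inflation from omitting baseline: √(V₀ / V₁)
- Carry-through of a 0.3 SD baseline imbalance when baseline is omitted: 0.3ρ

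| ρ | V₀ | V₁ | V₁/V₀ | SE inflation | Carry-through |
|---|---|---|---|---|---|
| 0.3 | 2.8/7 = 0.400 | 0.400 − 0.09 = 0.310 | 0.775 | 1.14 | 0.09 SD |
| 0.5 | 4.0/7 = 0.571 | 0.571 − 0.25 = 0.321 | 0.562 | 1.33 | 0.15 SD |
| 0.7 | 5.2/7 = 0.743 | 0.743 − 0.49 = 0.253 | 0.340 | 1.71 | 0.21 SD |

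**Single-visit contrast.** The variance ratio is 1 − ρ² = 0.91, 0.75 and 0.51, so the SE inflation is 1/√(1 − ρ²) = 1.05, 1.15 and 1.40. The loss is smaller than for the average but in the same direction.

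**Power for the average effect** (0.4 SD, two-sided 0.05, ρ = 0.3 / 0.5 / 0.7). At 33 per arm, adding baseline raises power from 73% to 83%, from 58% to 82%, and from 47% to 90%. At 99 per arm it rises from 99.4% to 99.9%, from 96.1% to 99.9%, and from 90.4% to about 100%. The omission therefore matters mainly because the trial was cut short.

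**If baseline were a level of time.** The comparison becomes a change score with variance V₀ + 1 − 2ρ = 0.800, 0.571 and 0.343. Its SE is 1.61, 1.33 and 1.16 times that of the baseline-adjusted analysis. The same 0.3 SD imbalance then carries through as 0.3(ρ − 1) = −0.21, −0.15 and −0.09 SD. This is partial adjustment and still less precise than a covariate.

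**Treatment-by-time test.** Baseline and site are constant within a subject, so as main effects they cannot alter the within-subject comparison on complete data. A check on one simulated data set (99 subjects, seven visits) gave F = 0.500837 both with and without them. Only a baseline-by-visit term can change this test.

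**Site.** Simulation used 21 sites (SAP 1.1), site-stratified 1:1:1 allocation, 33 per arm and ρ = 0.5. Adding site as a fixed effect on top of baseline moved the SE from 0.140 to 0.144 with no intra-site correlation, and from 0.140 to 0.137 with an assumed intra-site correlation of 0.1. That is about +3% or −2%.

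**The case against.** The strongest reply is that baseline adjustment is largely handled elsewhere. The repeated-measures model is an addition to ANCOVAs with baseline and site at all seven visits, and it lies outside the primary and key secondary testing. Under Protocol 5.2.4, subjects without at least a moderate response may receive other RA medication from Week 2, so the Day 8 ANCOVA is closer to the primary question than a seven-visit average. This stands and limits the consequence. It does not explain the omission, and it fails for raw DAS28 if the Kruskal-Wallis fallback is used.

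Four stronger readings are tempting, but the documents do not support them:

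- **That this is the only analysis using all visits.** The percentage-change model uses them too, with an outcome already expressed relative to baseline. So does time to first response: "Time to first EULAR response (moderate or good) will be analyzed using the Kaplan-Meier method".
- **That subjects with one missing visit will be dropped.** DAS28 with a missing component is set to missing ("then the DAS28 will be considered missing at that timepoint"), and SAP 4.2 adds "No other imputation of missing data will be performed, and only available data will be presented". Neither sentence prescribes complete-case fitting, and no fitting method is named. A retention figure would need visit-level missingness rates that the documents do not give. What stands is that the fitting method is unspecified.
- **That the time-course test is compromised.** On complete data the treatment-by-time test is unchanged by baseline or site main effects.
- **That omitting site costs precision.** The effect is small and of either sign. Site belongs in the model for consistency with the stratified randomisation.

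**Conclusion.** The omission is real and unexplained, and it is inconsistent with the ANCOVA in the same paragraph. If time means the post-baseline visits, the SE of the seven-visit average treatment effect is about 14% to 71% larger than with baseline adjustment, and a 0.3 SD baseline imbalance carries through as 0.09 to 0.21 SD. These figures rest on compound symmetry, equal variances and an assumed correlation of 0.3 to 0.7. The reading of time is also an inference, from the list of Weeks 1 to 12.

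The point covers the treatment main effect and visit-level contrasts of the DAS28 score model. It applies less directly to the percentage-change model. Because the analysis is supplementary, this is an improvement the plan should make. It does not threaten the trial's main conclusions.

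**What to change.** In SAP 4.8.3:

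- State that time means the post-baseline visits (Weeks 1, 2, 3, 4, 6, 8 and 12).
- Fit a likelihood-based mixed model to all available DAS28 values with treatment, visit, treatment-by-visit, baseline DAS28 and baseline-by-visit.
- Present contrasts of each Nanocort dose versus Depo-Medrol.
- Specify an unstructured covariance, and name in advance the simpler structure to use if it does not converge.
- Include site only in pooled form or as a random effect, for consistency with the stratification, without claiming a precision gain from it.

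The cost is a sentence or two of SAP text and a standard procedure in the SAS software already named; no new data are needed. There is a small downside. Baseline and baseline-by-visit add seven slope parameters, and an unstructured 7 × 7 covariance has 7 × 8 / 2 = 28 parameters, so convergence may fail in a reduced sample. That is why the fallback structure must be stated beforehand. Protocol 10.1 requires SAP approval before unblinding, so the change should be made by then.

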4.4 Sample size calculation

A total of 330 subjects will be enrolled and randomized into 3 groups of 110 subjects.

The EULAR response will be considered as primary parameter.

There is a special interest in the percentage of subjects with an EULAR response category of good or moderate (good and moderate combined) and the percentage of subjects with an EULAR response category of only good. These subjects will be called **EULAR responders** and **EULAR good-responders**, respectively.

Primary endpoint:

- the percentage of EULAR responders (good and moderate combined) at Day 8

Key secondary endpoints:

[figure not shown]
- The percentage of EULAR good-responders at Day 8
- The percentage of EULAR responders at Day 15
- The percentage of EULAR good-responders at Day 15

The sample size calculation for this study is based on group comparisons of EULAR responder rates (Nanocort 150 mg compared to Depo-Medrol® and Nanocort 75 mg compared to Depo-Medrol®) at Day 8. The study is called positive if one of the primary null hypotheses will be rejected.

The following primary null hypotheses will be considered:

$H_{0,1}$: EULAR responder rate at Day 8 for Nanocort 150 mg = EULAR responder rate at Day 8 for Depo-Medrol®

$H_{0,2}$: EULAR responder rate at Day 8 for Nanocort 75 mg = EULAR responder rate at Day 8 for Depo-Medrol®

Taking a drop-out rate of approximately 10% into consideration, a sample size of 110 subjects per treatment arm will be sufficiently large to show superiority of Nanocort compared to Depo-Medrol® in EULAR responders at Day 8 and to assess the safety of Nanocort in this study.

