10.4.3 Time to first EULAR response (moderate or good)

Time to first EULAR response, will be analyzed using the Kaplan-Meier method; comparison between treatment groups will be performed using the log-rank test.

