10.9 Missing Data

The handling of missing data for the clinical endpoints will be discussed in detail in the SAP.

For the primary endpoint EULAR response on Day 8, subjects who withdraw from the study before Day 8, because of insufficient efficacy will be considered as non-responders.

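### Time to first EULAR response: a subject who withdraws for insufficient efficacy before responding is, in effect, censored as still able to respond

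*Combined protocol and SAP*

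**What the plan says.** For this endpoint the SAP (4.8.3) says "Time to first EULAR response (moderate or good) will be analyzed using the Kaplan-Meier method" and "comparison between the treatment groups will be performed using the log-rank test". Protocol 10.4.3 says the same: "comparison between treatment groups will be performed using the log-rank test". Neither gives a censoring rule, a competing-event rule or a sensitivity analysis.

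Protocol 10.9 leaves the detail to the SAP: "The handling of missing data for the clinical endpoints will be discussed in detail in the SAP". SAP 4.2 imputes only partial adverse event dates and then states: "No other imputation of missing data will be performed, and only available data will be presented". If a DAS28 component is missing at a visit, "then the DAS28 will be considered missing at that timepoint" (SAP 4.8.3), so there is no EULAR response at that visit either.

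The only rule on leaving because treatment failed is in protocol 10.9. For the Day 8 primary endpoint, "subjects who withdraw from the study before Day 8, because of insufficient efficacy will be considered as non-responders". The SAP neither repeats this rule nor extends it to time to response.

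**The concern.** Kaplan-Meier assumes that a censored subject would have gone on to respond at the same rate as those still under observation. That is hard to defend for someone who left because the treatment was not working, and it departs from the principle the protocol adopts for its primary endpoint.

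Two things are at stake. First, the curve in Figure 1 and the estimates in Table 10.A would put the cumulative share of responders too high. Second, if more subjects leave one arm for failure, censoring takes those failures out of that arm's risk set. A difference in the share responding could then be hidden, or made to look larger than it is.

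**Working it through.** **What the documents supply.** Planned size is 110 per arm, with this allowance: "Taking a drop-out rate of approximately 10% into consideration" (protocol 4.4). No reasons for drop-out are given. EULAR response is assessed at Weeks 1, 2, 3, 4, 6, 8 and 12. The response rates behind the sample size are blacked out, and the number actually enrolled is not stated beyond being much less than planned (SAP 4.1). There is no figure of the plan's own to reproduce for this endpoint.

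**Assumptions.** Conditional response h at the seven visits: 55, 30, 20, 15, 12, 10 and 10%. Subjects who leave unresponded for failure make up 2.5, 5, 10 or 15% of those randomised. They leave either evenly after the first six visits or early (40/30/20/10% of them after Weeks 1 to 4). Where a reduced size is needed, 50 per arm is assumed.

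**Kaplan-Meier.** With leavers censored, 1-KM = 1 - product of (1 - h) = 1 - 0.45 × 0.70 × 0.80 × 0.85 × 0.88 × 0.90 × 0.90 = 1 - 0.153 = 84.7%, however many leave.

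**Leavers counted as non-responders.** Cumulative incidence = sum over visits of (share at risk × h). For 10% leaving early (shares are % of randomised):

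| Week | At risk | h | Respond | Leave after visit |
|---|---|---|---|---|
| 1 | 100.0 | 0.55 | 55.0 | 4.0 |
| 2 | 41.0 | 0.30 | 12.3 | 3.0 |
| 3 | 25.7 | 0.20 | 5.1 | 2.0 |
| 4 | 18.6 | 0.15 | 2.8 | 1.0 |
| 6 | 14.8 | 0.12 | 1.8 | 0 |
| 8 | 13.0 | 0.10 | 1.3 | 0 |
| 12 | 11.7 | 0.10 | 1.2 | 0 |

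The total is 79.5%, so the overstatement is 84.7 - 79.5, or 5.3 points before rounding.

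**Range.** Greenwood standard errors (SE) of the Kaplan-Meier estimate:

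| Leave for failure | Overstatement (even to early) | In SE, 110 per arm | In SE, 50 per arm |
|---|---|---|---|
| 2.5% | 0.9 to 1.3 points | below 0.5 | below 0.5 |
| 5% | 1.8 to 2.6 points | 0.50 to 0.73 | 0.34 to 0.49 |
| 10% | 3.6 to 5.3 points | 0.95 to 1.37 | 0.64 to 0.93 |

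A lower response set (40, 25, 15, 10, 10, 8, 8%) with 10% leaving early gives 4.4 points. With a constant hazard and 1-KM at Week 12 of 50 to 80%, the overstatement is 1.5 to 3.0 points at 5% leaving and 3.1 to 6.0 at 10%.

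**Between arms, hidden difference.** With early failure withdrawal of 5% in one arm and 15% in the other, and the same h, both Kaplan-Meier curves end at 84.7%. The shares responding are 82.1% and 76.8%, a gap of 5.3 points. The SE of that difference is √(0.821 × 0.179/110 + 0.768 × 0.232/110) = 5.4 points at 110 per arm, and 8.1 points at 50.

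**Between arms, log-rank simulation** (constant hazards, 4,000 runs, two-sided 0.05 assumed):

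| Leave for failure | 1-KM | Share responding | Rejection, censored / held as non-responders (110 per arm) | Same, 50 per arm |
|---|---|---|---|---|
| 5% v 20% | 70% v 70% | 67.6% v 60.2% | 4.8% / 15.4% | 5.0% / 10.2% |
| 15% v 5% | 80% v 65% | 71.0% v 62.8% | 73% / 37% | 41% / 20% |

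The first row hides a difference in the share responding. The second exaggerates one.

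**The case against.** The strongest objection is that few subjects may leave this way. Protocol 5.2.4 allows other RA medication for those without at least a moderate response from Week 2 and keeps them in the study. Protocol 8.3 asks early terminators back for the Week 12 assessments if possible, so some may supply a later result. Protocol 8.5 does not name lack of efficacy among its (non-exhaustive) reasons for withdrawal. All of this stands, and it puts the likely size at the low end.

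The large scenarios are demanding. Ten per cent leaving for failure is 10/45 = 22% of the assumed Week 1 non-responders, and 15% is one third of them. The protocol's drop-out figure covers all causes, so 10% for failure alone is an upper case.

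Four stronger readings are tempting, and the documents do not support them.

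- A reader might infer that the same person is a failure for the primary endpoint and still eligible to respond here. SAP 2.1 requires a post-baseline efficacy measurement for ITT, and the first scheduled one is Week 1. A subject who leaves before Day 8 is therefore normally outside this analysis, unless assessed at an early-termination visit. The inconsistency is one of principle.
- A reader might extend the point to withdrawals for adverse events. Protocol 10.9 names only insufficient efficacy, and nothing classes adverse event leavers as non-responders.
- A reader might infer that the log-rank test always favours the arm with more failures. In the equal-hazard example both curves end at the same value. The test remains valid for the hazard of response among those still observed. The bias in the share responding can go either way.
- A reader might take the SAP as prescribing this censoring. It does not use the word. Censoring follows from Kaplan-Meier on available data with no rule for holding leavers at risk.

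**Conclusion.** The concern holds in a limited form. For ITT subjects who withdraw for insufficient efficacy after a post-baseline assessment and before any response, the plan has the effect of censoring them as if they could still respond, contrary to the principle in protocol 10.9. The overstatement of the share responding is about 1 point at 2.5% failure withdrawal, 2 to 3 points at 5%, and 4 to 5 points if the whole drop-out were treatment failure. These figures rest on assumed visit-level response rates and assumed timing of withdrawal.

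Severity is minor. The endpoint is a non-key secondary outside the gatekeeping family, so the primary conclusion is untouched. The per-protocol table (10.B) is largely unaffected, because SAP 2.2 lists withdrawal before Week 12 as a likely exclusion. EULAR response by visit is reported separately in Table 9. How to count a response after other RA medication is a separate question, and this point does not depend on it.

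**What to change.** In SAP 4.8.3, for time to first EULAR response:

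- Keep subjects who withdraw for insufficient efficacy, or die, before first response in the risk set as non-responders to Day 85. Use any Week 12 assessment they return for.
- Treating these exits as a competing event, with cumulative incidence by arm and Gray's test, is equivalent except where a withdrawn subject returns at Week 12 with a response.
- Censor other withdrawals and administrative ends of follow-up at the last assessment.
- Show the planned Kaplan-Meier curve and log-rank test as a sensitivity analysis.
- Count adverse event withdrawals as non-response only in a further sensitivity analysis.

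The cost is a few sentences in the SAP and a few lines of code for Table 10.A and Figure 1. No new data are needed, because protocol 8.5 already requires the reason for withdrawal on the eCRF. The one downside is a slightly lower reported cumulative response. If few subjects left for failure, the two analyses will nearly agree, which is worth showing.
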